9. STATISTICAL ANALYSIS

9.1 Statistical Overview

The data will be reviewed by a Data Safety and Monitoring Board.

The Data Safety and Monitoring Board will be also responsible for:

· Determining whether information collected are sufficient to address the

objectives

 Recommending modifications to the statistical analysis plan to address additional research questions based on review of the data

9.2 Analysis Population

All patients who are successfully registered will be included in the analysis. A limit of one third of the entire population will be set for the group of Multivessel Disease patients treated with ABSORB and a conventional stent ("hybrid group").

9.3 Sample Size Calculations and Assumptions

Being this an observational registry aiming at quantifying effect estimates without direct comparisons to literature benchmarks, we relied on confidence interval profiling for sample size justification, without proceeding with formal power analysis. As the main analysis is a pooled analysis of patients with multivessel disease and/or long lesions, an overall and comprehensive analysis is planned as the primary analytical approach. Accordingly, we computed that a target sample of 1000 patients will enable the computation of reasonably precise 95% confidence intervals. Specifically, assuming a 4.2% MACE rate at 1 year (in keeping with ABSORBD EXTEND data), confidence intervals computed with the adjusted Wald method would be 3.1% to 5.6% for a 1000-patient sample (point estimate 42/1000 [4.2%]).

Given that the registry aims to reflect real-world patients and practice, no provision to limit or restrict patient enrolment depending on the presence of multivessel disease vs long lesions is envisioned.

9.4 Statistical Analyses

Continuous endpoints will be summarized by presenting the total number of patients, mean, standard deviation, median, minimum, and maximum. Tabulation of

categorical parameters will include counts and percentages. The outcomes will be summarized as both a discrete and a continuous variable using the method described above. Survival analysis will be performed with the Kaplan-Meier method. Statistical inference will be based on the computation of 95% confidence intervals using the adjusted Wald method. Additional analyses will involve key subgroups defined according to baseline, lesion, and procedural features, with statistical significance set at the 5% 2-tailed level. Specifically, Student t, Fisher exact, and logrank tests will be used for such bivariate analyses, whereas multivariable linear regression, logistic regression, and Cox proportional hazard analyses will be used to adjust for confounders. In addition, separate analyses for patients with only multivessel disease, patients with only long lesions, and patients with hybrid revascularization will be performed.

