5. OUTCOMES/ENDPOINTS

Outcomes are as specified below:

- **5.1 Primary**: the cumulative hierarchical incidence of major adverse cardiac events (MACE) defined as: cardiac death, non-fatal target vessel myocardial infarction (MI), or clinically driven target lesion revascularization (TLR);
- **5.2 Secondary endpoints:** All causes mortality, clinically driven TLR, clinically driven target vessel revascularization (TVR), any revascularisation (non TLR, non TVR) and ARC-defined stent thrombosis, at any time point. Any type of angina post procedure measured by means of the Cardio Test, proposed by the ANMCO (Associazione Nazionale Medici Cardiologic Ospedalieri) [21]
- **5.3 Efficacy parameters**: TLR and TVR up to 5-year follow-up.
- **5.4 Safety "patient oriented" parameters:** all cause mortality, any myocardial infarction, Stent thrombosis based on the ARC classification, up to 5-year follow-up. Data on dual antiplatelet therapy use will also be collected and analyzed.

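### Kaplan-Meier is the only time-to-event incidence estimator named, so 5-year TLR, TVR, other revascularisation and stent thrombosis curves would somewhat overstate cumulative incidence if deaths are censored (minor)

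*Protocol*

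**What the plan says.** Section 9.4 states: "Survival analysis will be performed with the Kaplan-Meier method". The synopsis repeats this. No other method for estimating incidence over time is named. Log-rank tests serve subgroup comparison, and the regression models, including Cox, are there for adjustment: "multivariable linear regression, logistic regression, and Cox proportional hazard analyses will be used to adjust for confounders".

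Section 9.4 does not rest the reported rates on Kaplan-Meier alone. Tabulation of "categorical parameters will include counts and percentages", and "The outcomes will be summarized as both a discrete and a continuous variable using the method described above". The sentence straight after the Kaplan-Meier one reads: "Statistical inference will be based on the computation of 95% confidence intervals using the adjusted Wald method". Section 9.3 sizes the registry on such a proportion, 42/1000 at 1 year.

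Section 5 fixes the outcomes and horizons. Efficacy is "TLR and TVR up to 5-year follow-up". Safety is "all cause mortality, any myocardial infarction, Stent thrombosis based on the ARC classification, up to 5-year follow-up". Other revascularisation is a secondary endpoint in 5.2, and follow-up runs to 5 years (4.3). The primary MACE composite is "cardiac death, non-fatal target vessel myocardial infarction (MI), or clinically driven target lesion revascularization (TLR"; 5.1 gives it no time point.

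**The concern.** 1-KM equals cumulative incidence only if nothing other than the event itself takes patients permanently out of risk. Among the outcomes in section 5, all-cause mortality meets that condition. TLR, TVR and other revascularisation contain no death component, and stent thrombosis is in the same position so far as a death is not itself adjudicated as one. Censoring at death treats the dead as if they could still have the event later at the same rate as the survivors. The estimate then answers a hypothetical question, what would happen if nobody died, and lies above the share of patients who actually have the event. The gap grows with follow-up and with mortality.

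At stake is how far the 5-year curves can be read as the risk a patient faces. The registry has no comparator and exists to quantify rates, so the level of each curve matters.

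**Working it through.** **1. The plan's own figure.** Adjusted Wald for 42/1000 (section 9.3), z = 1.96: n~ = 1000 + 3.84 = 1003.84; p~ = (42 + 1.92)/1003.84 = 4.375%; half-width = 1.96 × sqrt(0.04375 × 0.95625/1003.84) = 1.27 points. The interval is 3.11% to 5.64%, which matches the stated 3.1% to 5.6%. It uses a count and a full denominator, in which patients who die without the event remain.

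**2. Inputs for the 5-year check.** From the protocol: n = 1000 and 5 years of follow-up. Assumed, because the protocol gives no 5-year rates: true event incidence F, competing death D, constant cause-specific hazards, complete follow-up.

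**3. Formula.** Total hazard over 5 years H = −ln(1 − F − D); event share h = H × F/(F + D); 1-KM = 1 − exp(−h). For F = 10%, SE = sqrt(0.10 × 0.90/1000) = 0.949 points.

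| D at 5 years | H | h | 1-KM | Excess (points) | Excess / SE |
|---|---|---|---|---|---|
| 5% | 0.1625 | 0.1083 | 10.27% | 0.27 | 0.28 |
| 10% | 0.2231 | 0.1116 | 10.56% | 0.56 | 0.59 |
| 15% | 0.2877 | 0.1151 | 10.87% | 0.87 | 0.92 |

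If D is instead the death probability in the absence of the event, 1-KM is 10.25%, 10.53% and 10.82%, which is nearly the same.

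**4. Scale.** The adjusted Wald half-width for 10% at n = 1000 is 1.87 points, so every excess above lies inside it. It is still not nothing: a 95% interval of that width centred on 1-KM would cover the true incidence with probability Φ(1.96 − 0.59) − Φ(−1.96 − 0.59), about 91%, at D = 10%, and about 85% at D = 15%.

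**5. A rarer event, such as stent thrombosis.** For F = 3% and death of 5%, 10% or 15% (second definition of D), 1-KM is 3.08%, 3.16% or 3.25%. The excess is 0.08 to 0.25 points, against a half-width of 1.09.

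**6. MACE at 1 year.** Cardiac death is a component, so only non-cardiac death competes. With a true rate of 4.2% and non-cardiac death of 0.5% to 3% (assumed), 1-KM is 4.21% to 4.26%. The excess is 0.01 to 0.06 points, against a half-width of 1.27.

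**The case against.** The strongest reply is that the registry's inference does not use Kaplan-Meier. It uses adjusted Wald intervals on proportions, and competing death does not inflate those. This stands. A reader might infer that the registry's reported incidence, or its main result, is too high; section 9.4 does not support that.

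The crude proportion does not settle the 5-year question, however. Section 6.4 stops recording at withdrawal, allows for loss to follow-up and does not replace patients, while 9.2 analyses everyone registered. With losses kept in the denominator the proportion runs low. Under the same assumptions (true 10%, death 10%) and loss of 5%, 10% or 15% over 5 years, it is about 9.8%, 9.5% or 9.3%. At 10% loss, for example, the loss hazard is 0.1054 and the total hazard 0.1116 + 0.1116 + 0.1054 = 0.3285, so the proportion is (0.1116/0.3285) × (1 − exp(−0.3285)) = 9.5%. The two named summaries thus err in opposite directions.

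Secondly, the text does not say that deaths are censored, and such detail is often left to a statistical analysis plan, which 9.1 mentions and which is not at hand. This stands in part: censoring is inferred from default use. But the protocol itself names the estimator, in two places, and names no alternative.

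Two further readings are tempting. One is that the MACE estimate is materially biased. Its only planned horizon is 1 year, where the effect is negligible, and the protocol gives no 5-year MACE rate for this registry. The other is that subgroup comparisons are distorted. Fisher tests work on proportions, and log-rank and Cox compare cause-specific hazards, for which censoring deaths is standard. Nothing in the document quantifies such a distortion.

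**Conclusion.** The point holds as a minor one, limited to the 5-year curves for TLR, TVR, other revascularisation and stent thrombosis. The direction is certain if deaths are censored. The size, roughly 0.3 to 0.9 points on a true 10%, depends on assumed competing death of 5% to 15% and constant hazards, and stays below the interval half-width. Should 5-year mortality be at the low end of that range, the effect is of little consequence. No figure stated in the protocol changes, and neither the sample size justification nor the adjusted Wald inference is affected.

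**What to change.** In section 9.4 and the synopsis, state that the 5-year cumulative incidence of TLR, TVR, other revascularisation and stent thrombosis is estimated by the Aalen-Johansen method with death as the competing event, with its 95% confidence interval. If MACE is reported beyond 1 year, use the same estimator with non-cardiac death competing. This estimator handles both death and loss to follow-up. Keep Kaplan-Meier for all-cause mortality and as a supportive display, and keep the log-rank tests and cause-specific Cox models as planned.

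The cost is a sentence in each place. All-cause and cardiac death are already endpoint data, so nothing new is collected. The one small downside is that the main rates would not be strictly like-for-like with published 1-KM figures; the supportive Kaplan-Meier display covers that.

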6.4 Patient Discontinuation

Once registered, each patient shall remain in the registry until completion of the required follow-up period; however, a patient's participation is voluntary and the patient has the right to withdraw at any time without penalty or loss of benefit. Conceivable reasons for discontinuation may include but not be limited to the following:

- Patient voluntary withdrawal
- Patient withdrawal by physician as clinically-indicated
- Patient lost-to-follow-up: If the patient misses two consecutive scheduled follow up time points, and attempts at contacting the patient are unsuccessful, then the patient is considered lost to follow-up.

No additional data is needed and will be recorded from patients once withdrawn from the registry. Patients will not be replaced.

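### The adjusted Wald interval named for the overall MACE estimate cannot handle incomplete follow-up, so it is not valid at the later time points of a 5-year registry

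*Protocol*

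**What the plan says.** Protocol section 9.4 makes two statements in succession: "Survival analysis will be performed with the Kaplan-Meier method", and then "Statistical inference will be based on the computation of 95% confidence intervals using the adjusted Wald method". No interval method is attached to the Kaplan-Meier estimate. The analytical plan in the synopsis carries the same pair and applies the adjusted Wald interval to the overall estimate. Section 9.4 also sets out subgroup and adjusted analyses, "with statistical significance set at the 5% 2-tailed level": t, Fisher and log-rank tests, and "multivariable linear regression, logistic regression, and Cox proportional hazard analyses will be used to adjust for confounders".

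Section 9.3 shows how the interval is meant to be used: "assuming a 4.2% MACE rate at 1 year (in keeping with ABSORBD EXTEND data"), 42 events in 1000 patients give 3.1% to 5.6%. This calculation has no allowance for loss.

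On who is analysed, section 9.2 says "All patients who are successfully registered will be included in the analysis". On incomplete follow-up, section 6.4 allows for withdrawal and loss, rules out replacement, and states "No additional data is needed and will be recorded from patients once withdrawn from the registry". Follow-up runs to 5 years (4.3), the objective is long-term performance (3), and the efficacy and safety parameters extend to 5 years (5.3, 5.4).

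**The concern.** Adjusted Wald is an interval for x events among n patients whose outcome is known. A patient who leaves at year 2 without an event has no known 5-year status. Kaplan-Meier uses the two years observed and then censors the patient; a binomial interval must count the patient as event-free or leave the patient out. The method named for inference therefore does not match the estimator named beside it, or the follow-up that section 6.4 foresees.

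The main output of this single-arm registry is a MACE rate with its interval. If that interval is centred on the wrong value at 3 or 5 years, its stated 95% confidence does not hold, and the same applies to TLR, TVR and stent thrombosis.

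**Working it through.** **1. The plan's own figure.** With z = 1.96, x = 42 and n = 1000, the adjusted estimate is (x + z²/2)/(n + z²) = 4.38%. The interval is that estimate ± z·√[p(1−p)/(n + z²)], which gives 3.11% to 5.64%. The stated 3.1% to 5.6% reproduces. Plain Wald (2.96% to 5.44%) does not, so the intended method is clear: a binomial interval with all 1000 patients in the denominator.

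**2. Inputs for later time points.** The protocol gives no loss rate and no 5-year MACE rate, so both are assumptions. For the risk, I carry forward the 3-year MACE figure of 10.0% that section 2.2 reports for Cohort B, at constant hazard:

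- h = −ln(0.90)/3 = 0.0351 per year
- true 5-year risk = 1 − exp(−5h) = 16.1%

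Loss is taken as non-informative at constant rate d, with n = 1000.

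**3. The two available binomial denominators at 5 years.** Let S = exp(−5(h + d)), the share followed to 5 years without an event.

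- All registered patients: A = h/(h + d) × (1 − S)
- Patients with an event or complete follow-up only: B = A/(A + S)

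For d = 0.02, S = 0.759, so A = 0.0351/0.0551 × 0.241 = 15.3% and B = 0.1535/(0.1535 + 0.759) = 16.8%.

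Coverage is the exact binomial probability, with event probability A, that the adjusted Wald interval on 1000 patients contains 16.1%.

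| Loss per year | A: all registered | Coverage using A | B: event or complete follow-up |
|---|---|---|---|
| 0.5% | 15.9% | 94.6% | 16.3% |
| 1% | 15.7% | 93.7% | 16.5% |
| 2% | 15.3% | 90% | 16.8% |
| 3% | 15.0% | 84% | 17.2% |
| 5% | 14.3% | 65% | 18.0% |

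The two choices err in opposite directions, and neither recovers 16.1%.

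**4. A different assumed risk.** Carrying 4.2% per year forward gives 1 − 0.958⁵ = 19.3% at 5 years. With all registered patients in the denominator:

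- 10% cumulative loss: 18.4% (16.1 to 20.9)
- 20% cumulative loss: 17.4% (15.2 to 19.9)
- 30% cumulative loss: 16.3% (14.1 to 18.7), which excludes the assumed 19.3%

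A Kaplan-Meier estimate with a Greenwood interval stays centred on 19.3% (16.7 to 21.9 at 20% loss). If the 5-year risk is only 10%, losses of 10% to 20% give 9.5% to 9.0%.

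**5. At 1 year.** With a true rate of 4.2% and 5% loss, the all-registered proportion is 4.1% and coverage is about 95%. The effect is negligible.

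**The case against.** The strongest reply is that section 9.4 already contains methods that handle censoring, and that the rest is detail for a statistical analysis plan. Several parts of this reply stand.

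- **Adjusted Wald is not the only inferential method.** A reader might infer this from 9.4, but log-rank tests and Cox regression are named too. They serve the subgroup and adjusted analyses. Adjusted Wald is the only interval named for the overall estimate.
- **The protocol does not say that lost patients count as event-free.** A reader might combine 9.2 with the 42/1000 calculation and conclude that the rate will be too low, in the device's favour. But 9.2 defines who is analysed, and a Kaplan-Meier analysis also includes every registered patient. The binomial denominator under incomplete follow-up is left open, so the direction of bias is open as well.
- **The size depends on assumptions.** With loss at or below 1% per year, little is wrong. At 1 year, the only horizon at which the protocol works the interval through, it performs properly.
- **Physician withdrawal is not shown to be informative.** Section 6.4 lists "Patient withdrawal by physician as clinically-indicated" among conceivable reasons for discontinuation. A reader might infer that it follows deterioration and would bias Kaplan-Meier too. Nothing in the protocol says so or how often it would occur, so it does not support a demand to delete that reason.

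The reply does not remove the central point. A later plan could define the denominator, but step 3 shows that neither binomial denominator gives the right answer at 5 years. The protocol has named a method that does not fit its follow-up, which is more than leaving a detail open.

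**Conclusion.** The concern holds as a mismatch between a stated method and the design. Adjusted Wald is sound for the 1-year planning calculation and for proportions with complete data. It is not valid for the overall MACE estimate at later time points once some patients have unknown status. The illustrated error at 5 years is about 1 to 2 points downward or upward, depending on the denominator, at losses of 2% to 5% per year. Coverage with all registered patients falls to between 90% and 65%. These figures rest on an extrapolated 16.1% risk, constant hazards, non-informative loss and n = 1000, none of which the protocol gives for 5 years. Since the effect is small at low loss and the direction is not fixed, this should be fixed but does not undermine the registry.

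**What to change.** In section 9.4 and the synopsis, state that the 95% confidence interval for MACE and its components at each follow-up time point comes from the time-to-event estimate: Kaplan-Meier or cumulative incidence, time to first event, censored at last contact, with a Greenwood-type interval on the log-log scale. Keep adjusted Wald for in-hospital results and other proportions where every patient's status is known. The sample-size calculation in 9.3 can stay as it is.

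The text should also say which of the two estimators is used. Treating non-cardiac death as censoring rather than as a competing event would raise the 5-year figure by about 0.4 to 0.8 points if such deaths run at 1% to 2% per year (16.1% against 15.7% and 15.3%). This is a refinement, not a condition of the fix.

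The cost is wording in two places and standard software output, with no extra patients. Intervals become slightly wider, because they then reflect the information lost through incomplete follow-up.

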10. DIRECT ACCESS TO SOURCE DATA/DOCUMENTS

The investigator/institution will permit direct access to source data/documents in order for registry-related monitoring, audits, MEC review, and regulatory inspections to be performed.

As part of the informed consent, the investigator or designee will obtain permission for registry monitors or regulatory authorities to review, in confidence, any records identifying the patients in this registry.

11. QUALITY CONTROL AND QUALITY ASSURANCE

11.1 Protocol and Informed Consent Approval

The Principal Investigator at each site must confirm and agree with the content of the protocol prior to participation in this registry. Also, the Principal Investigator will obtain written approval of the protocol, informed consent form, and other registry related documents from the MEC. In addition, the investigator will take actions

necessary for ongoing registry approval at their site per established procedures of the MEC.

The investigator will advise the MEC of the progress of this registry on a regular basis until registry completion as required by the MEC.

The investigator will submit any amendments to the protocol as well as associated informed consent form changes and obtain written MEC approval prior to implementation as required by the MEC.

11.2 Monitoring

A monitoring plan will be established. Remote monitoring by the CRO and source documents analysis for events throughout the study period by an independent Event Committee, will be conducted to ensure compliance with the protocol and applicable regulatory requirements.

12. DATA HANDLING AND RECORD KEEPING

For the registry duration, the investigator will maintain complete and accurate documentation including but not limited to the following: medical records, registry progress records, laboratory reports, electronic case report forms, signed informed consent forms, device serial numbers for monitoring malfunctions, correspondence with the MEC and registry monitor/Sponsor, SAE reports, and information regarding patient discontinuation or registry completion.

12.1 Source Documentation

 Medical history/physical condition of the patient before involvement in the registry sufficient to verify protocol entry criteria

- Dated and signed notes on the day of entry into the registry referencing the sponsor, protocol number, patient ID number and a statement that informed consent was obtained
- Dated and signed notes from each patient visit
- Adverse events reported and their resolution including supporting documents such as discharge summaries, catheterization laboratory reports, ECGs, and lab results including documentation of site awareness of SAEs and of investigator device relationship assessment of AEs.
- Notes regarding Dual Anti Platelet Therapy medications taken during the registry
- (including start and stop dates)
- Patient's condition upon completion of or withdrawal from the registry
- Any other data required to substantiate data entered into the CRF

12.2 Electronic Case Report Form Completion

Primary data collection based on source-documented hospital and /or clinic chart reviews will be performed clearly and accurately by site personnel trained on the protocol and eCRF completion. eCRF data will be collected for all patients that are registered.

13. ETHICAL CONSIDERATION

13.1 Medical Ethics Committee Review

Medical Ethics Committee (MEC) approval for the protocol and informed consent form /other written information provided to the patient will be obtained by the Principal Investigator at each investigational site prior to participation in this registry. No changes will be made to the protocol or informed consent form or other written information provided to the patient without appropriate approvals by the MEC.

Until the registry is completed, the Investigator will advise his/her MEC of the progress of this registry, per MEC requirements.

Further, any amendments to the protocol as well as associated informed consent form changes will be submitted to the MEC and written approval obtained prior to implementation, according to each institution's MEC requirements.

